7.1.4.8.1 Best Overall Response (RECIST 1.1)

The best overall response is the best response recorded from the start of the study treatment until the end of treatment taking into account any requirement for confirmation. The patient's best overall response assignment will depend on the findings of both target and non-target disease and will also take into consideration the appearance of new lesions (Table 10).

Table 10 Best Overall Response (RECIST 1.1)

Target Lesions	Non-Target Lesions		Overall Response
	Baseline Lesions	Unequivocal New Lesions	
Baseline (Index) and New Measurable Lesions	CR	No	CR

Target Lesions Baseline (Index) and New Measurable Lesions	Non-Target Lesions		Overall Response
	Baseline Lesions	Unequivocal New Lesions	
CR	Non-CR/Non-PD	No	PR
CR	NE	No	PR
PR	Non-PD or NE	No	PR
SD	Non-PD or NE	No	SD
Not all evaluated	Non-PD	No	NE
PD	Any	Yes or No	PD
Any	PD	Yes or No	PD
Any	Any	Yes	PD

CR = complete response; NE = not evaluable at a particular time point; PR = partial response; SD = stable disease; PD = progressive disease

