5.10 Treatment after Initial Evidence of Radiologic Disease Progression

Immunotherapy may produce antitumor effects by potentiating endogenous cancer-specific immune response. The response patterns seen with such an approach may extend beyond the typical time course of responses seen with cytotoxic agents and can manifest as a clinical response after an initial increase in tumor burden or even the appearance of new lesions. If radiological imaging shows progressive disease (PD), subjects may continue on study with the option of continuing treatment, provided there is:

- no deterioration in ECOG performance status
- absence of signs and symptoms (including worsening of laboratory values) indicating disease progression
- absence of rapid progression of disease
- absence of progressive tumor at critical anatomical sites (e.g., cord compression) requiring urgent alternative medical intervention

Tumor assessment should be repeated ≥ 4 weeks later to confirm PD. If repeat imaging shows CR, partial response (PR) or stable disease (SD) compared to the baseline scan, treatments may be continued or resumed. If repeat imaging shows continued progression

of disease, subjects will be discontinued from study therapy, unless the basis for the PD assessment is enlarged tumor-draining lymph nodes in the presence of a target tumor reduction. In determining whether or not tumor burden has increased or decreased, Investigators should consider all target lesions as well as non-target lesions.

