7.1.4.8 Overall Response

Overall response will be determined based on RECIST 1.1 criteria and by irRECIST criteria (Table 9). Overall response according to irRECIST is derived from the responses in measurable lesions (based on TMTB) and the presence of any non-measurable lesions.

Table 9 Tumor Response Evaluation: Comparison of RECIST 1.1 and irRECIST

Criteria	RECIST1.1	irRECIST
New measurable lesions (≥ 10 mm)	Always represents PD	Incorporated into tumor burden

Criteria	RECIST1.1	irRECIST
New non-measurable lesions (< 10 mm)	Always represents PD	Does not define progression but precludes irCR
Non-Target lesions	Changes contribute to defining BOR of CR, PR, SD, and PD	Contribute to defining irCR (complete disappearance required)
CR	Disappearance of all lesions	Disappearance of all lesions
PR	≥ 30% decrease in the sum of the longest diameter of all target lesions compared with baseline, in absence of new lesions or unequivocal progression of non-target lesions	≥ 30% decrease in tumor burden compared with baseline
SD	Neither sufficient shrinkage to qualify for PR nor sufficient increase to qualify for PD, taking as reference the smallest sum diameters while on study	Neither a 30% decrease in tumor burden compared with baseline nor a 20% increase compared with nadir can be established
PD	At least 20% increase in sum of diameters of target lesions, taking as reference the smallest sum on study. In addition to the relative increase of 20%, the sum must also demonstrate an absolute increase of at least 5mm. The appearance of one or more new lesions is also considered progression.	At least 20% increase in tumor burden compared with nadir (at any single time point) ^a

irRECIST = immune-related Response Evaluation Criteria in Solid Tumors; BOR = best overall response; CR = complete response; irCR = immune-related complete response; PD = progressive disease; PR = partial response; SD = stable disease;

^a Patients with an initial finding of progressive disease (irPD) before or at the 8-week imaging assessment, but without rapid clinical deterioration, require confirmation of irPD with a second, consecutive scan obtained ≥ 4 weeks from the initiation documentation. Patients will continue to receive study treatment until irPD is confirmed at this later time point. Best overall response (BOR) will therefore include responses occurring at any time before disease progression and after early progression (i.e., within the first 9 weeks of the study).

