7.1.4.8.2 Immune-Related Best Overall Response (irRECIST)

The immune-related best overall response (irBOR) is the best irRC overall response over the study as a whole, recorded between the date of first dose until the last tumor assessment prior to subsequent therapy (including tumor resection surgery) for the individual subject in the study (Table 11). As with the primary definitions of tumor response, early progression (i.e., irPD occurring prior to Week 8) will not preclude an irBOR of irCR, irPR or irSD resulting from the Week 8 assessment. An assessment of irPD at or after Week 8 will preclude a subsequent irBOR of irCR, irPR or irSD. However, any post-progression clinical activity in subjects with irBOR of irPD may be summarized for exploratory purposes.

Table 11 Immune-Related Best Overall Response (irBOR)

Target Lesions Baseline (Index) and New Measurable Lesions	Non-Target Lesions ^a		irRC Overall Response
	Total Measurable Tumor Burden	Baseline Lesions	
irCR	irCR	No	irCR
irCR	irSD	No	irPR
irPR	irCR or irSD	No	irPR
irSD	irCR or irSD	No	irSD

Target Lesions Baseline (Index) and New Measurable Lesions	Non-Target Lesions ^a		irRC Overall Response
	Total Measurable Tumor Burden	Baseline Lesions	
irPD	Any	Yes or No	irPD
Any	Unequivocal Progression	Yes or No	irPD
Any	Any	Yes	irPD

irCR = immune-related complete response; irPR = immune-related partial response; irSD = immune-related stable disease; irPD = immune-related progressive disease

^a Any increase in the size or number of non-measurable lesions does not necessarily imply an overall response of irPD. If these lesions become measurable (≥ 10 mm) at a subsequent assessment, their measurement will at that point start to contribute to the total measurable tumor burden. To achieve unequivocal progression of non-target lesions, there must be substantial worsening in non-target disease that is of a magnitude that the Investigator feels it is important to change therapy. Equivocal findings of progression of non-target lesions (e.g., small and uncertain new lesions; cystic changes or necrosis in existing lesions) should be considered irSD, and treatment may continue until the next assessment.

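### As written, a RECIST 1.1 response seen on treatment after a progression that has reversed can count in the primary response rate

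*Combined protocol and SAP*

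**What the plan says.** Overall tumor response by RECIST 1.1 is a primary endpoint (Section 8.3.1) and one of two routes through the Stage 1 gate (Sections 2 and 8.2).

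- **Window for RECIST 1.1 (7.1.4.8.1):** "The best overall response is the best response recorded from the start of the study treatment until the end of treatment". The assignment also depends on target and non-target findings and "will also take into consideration the appearance of new lesions", through Table 10.
- **Treatment after progression (5.10):** "If radiological imaging shows progressive disease (PD), subjects may continue on study with the option of continuing treatment", under listed clinical conditions. On the scan that follows: "If repeat imaging shows CR, partial response (PR) or stable disease (SD) compared to the baseline scan, treatments may be continued or resumed". Section 5.8 lists progression as a reason for which a subject can be discontinued, so PD does not by itself end treatment.
- **Cut-off for irRECIST (7.1.4.8.2):** "An assessment of irPD at or after Week 8 will preclude a subsequent irBOR of irCR, irPR or irSD". Activity after that point may be summarized as exploratory.
- **Early progression (7.1.4.8.2):** "As with the primary definitions of tumor response, early progression (i.e., irPD occurring prior to Week 8) will not preclude an irBOR" of response or stable disease from the Week 8 assessment.
- **Table 9, footnote a (7.1.4.8):** "Best overall response (BOR) will therefore include responses occurring at any time before disease progression and after early progression", with early progression meaning the first 9 weeks. The footnote hangs on the irRECIST PD cell but speaks of BOR, not irBOR.
- **RECIST 1.1 PR (Table 9):** requires the fall in target lesions "in absence of new lesions or unequivocal progression of non-target lesions".

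**The concern.** A conventional response rate should not collect responses that appear after conventional progression. In this protocol irRECIST is the separate, secondary measure meant for that pattern. The RECIST 1.1 window ends with treatment, and treatment may outlast progression, so the primary measure can take in some of what the secondary one was added to describe.

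The response rate is judged against fixed thresholds in a single-arm, open-label study, with few responders expected near the Stage 1 limit. A definition that can only add responders moves the result towards continuing. It also means that one subject can be a PFS event at one scan and a responder at a later one. That is a consequence of the same wording and not a separate defect.

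**Working it through.** **1. The passages side by side.** The protocol gives no figure to reproduce here, so the first check is textual.

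| Question | RECIST 1.1 (primary) | irRECIST (secondary) |
|---|---|---|
| When does the best-response window end? | End of treatment (7.1.4.8.1) | Last assessment before subsequent therapy (7.1.4.8.2) |
| Does progression bar a later response? | No sentence in 7.1.4.8.1, Table 10 or 8.3.1 | Yes, for irPD at or after Week 8 |
| Can treatment go on after PD? | Yes (5.10) | Yes (5.10; Table 9 footnote a) |

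Take a subject with RECIST 1.1 PD at one scan who continues under 5.10 and has a PR on the next on-treatment scan. Both scans lie inside the window. Table 10 grades combinations of findings and has no rule on their order, so the best of the two is PR. The reference to any confirmation requirement does not prevent this, because the protocol states none for CR or PR.

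**2. Who can be affected.** Tables 9 and 10 keep a visit at PD while an unequivocal new lesion or non-target PD is present. Only a PD that reverses can matter: target growth followed by a fall of at least 30% from baseline, or new lesions that disappear.

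**3. How far the early-progression wording narrows this.** If footnote a and the opening clause of the 7.1.4.8.2 sentence also govern RECIST 1.1, only responses after PD in the first 9 weeks are added. The first scheduled scan is at Week 8 (plus or minus 1 week), so PD on that scan would usually qualify. The two passages also disagree on that scan for irRECIST: footnote a treats irPD up to and including the 8-week scan as early, while 7.1.4.8.2 treats irPD at Week 8 as a bar.

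**4. Weight of one subject.**

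- Stage 1: 1/31 = 3.2 points. 3/31 = 9.7% misses the 10% rule; 4/31 = 12.9% meets it.
- Both stages: 1/55 = 1.8 points. 13/55 = 23.6% and 14/55 = 25.5% lie on either side of the 25% in the Stage 2 hypotheses.

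**5. Illustration for the response limb of Stage 1.** Section 8.2 gives n = 31 and two versions of the rule: a rate of at least 10%, which means 4 or more of 31, and 3 or more responses. The documents give no rate of response after PD. Assumptions: a true rate before PD of 8% or 5%, with 2 to 5 percentage points added by responses after PD.

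P(X ≥ c) = 1 − Σ C(31,k) p^k (1−p)^(31−k), summed over k = 0 to c−1.

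For p = 0.08 the terms for k = 0 to 3 are 0.0754, 0.2033, 0.2651 and 0.2229. So P(X ≥ 4) = 1 − 0.7667 = 0.233 and P(X ≥ 3) = 1 − 0.5438 = 0.456.

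| Rate before PD | Added points | p | P(≥4/31) | P(≥3/31) |
|---|---|---|---|---|
| 8% | 0 | 0.08 | 0.233 | 0.456 |
| 8% | 2 | 0.10 | 0.376 | 0.611 |
| 8% | 5 | 0.13 | 0.586 | 0.786 |
| 5% | 0 | 0.05 | 0.067 | 0.201 |
| 5% | 2 | 0.07 | 0.169 | 0.371 |
| 5% | 5 | 0.10 | 0.376 | 0.611 |

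The rise appears under either version of the rule.

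**The case against.** A reader might infer that every response after progression enters the primary rate. The documents do not support that. No sentence says so, 5.10 governs dosing rather than endpoint derivation, and Tables 9 and 10 hold a visit at PD while new lesions or non-target progression persist. Section 5.10 also asks for stable performance status, no symptoms of progression and no rapid progression. Its draining-node exception applies only alongside target reduction. These limits stand, and they shrink the group without emptying it.

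A second objection is that the window is already restricted, because footnote a speaks of BOR in general and 7.1.4.8.2 refers to the primary definitions. This may be right. The footnote is attached to an irRECIST cell, so its reach is uncertain, and even on that reading responses after early PD still count.

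A third is that Section 12.3 adopts RECIST 1.1 and Section 8.1 leaves analysis details to an SAP. Neither supplies a cut-off in the documents available, while 7.1.4.8.1 writes out a specific window that a programmer would follow.

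A fourth is that the size is conjecture and the decision need not change. The size is indeed unknown. A reader might take 3/31 as a plain Stage 1 failure, but Section 8.2 also speaks of 3 or more responses, under which it passes. A 6-month PFS rate of at least 20% may open the gate whatever the response count.

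**Conclusion.** The point holds in limited form. Applied as written, the RECIST 1.1 rule lets a CR or PR after a reversed RECIST 1.1 PD count in the primary response rate. At the narrowest plausible reading this applies to PD in the first 9 weeks; at the widest, to any reversed PD while treatment continues. The effect can only be upward.

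A reader might conclude that the primary measure is looser than irRECIST throughout. That goes too far: RECIST 1.1 still calls PD on any new lesion, and the irRECIST cut-off is itself inconsistent at the Week 8 scan. The contrast is that irRECIST states a bar after progression and RECIST 1.1 does not.

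One subject is worth 3.2 points in Stage 1 and can decide the response limb. The probabilities above rest on assumed rates of 5% or 8% before PD and 2 to 5 added points. They describe that limb alone and do not estimate what will happen in this trial.

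**What to change.** 1. In 7.1.4.8.1, end the RECIST 1.1 best-response window at the first RECIST 1.1 PD or the start of other anticancer therapy, whichever is earlier. State that, for analysis, PD is dated at the first scan that meets it, whether or not dosing continues or a repeat scan is done.
2. State that Table 9 footnote a applies to irRECIST only, and write irBOR there.
3. In 7.1.4.8.2, delete the opening clause that ties the early-progression rule to the primary definitions.
4. Reconcile footnote a with 7.1.4.8.2 on whether irPD at the 8-week scan is early progression or a bar to later response.
5. Report responses after RECIST 1.1 PD under irRECIST where they qualify, or in an exploratory listing.

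Changing 7.1.4.8.1 alone would leave the other two passages open to being read against it. The changes should be made before the Stage 1 interim analysis, because in an open-label study a later choice could be influenced by the data.

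The cost is a few sentences and one derivation, with no new data. The reported RECIST 1.1 rate may be slightly lower. The treatment rules in 5.10 are unchanged.

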7.1.4.8.2 Immune-Related Best Overall Response (irRECIST)

The immune-related best overall response (irBOR) is the best irRC overall response over the study as a whole, recorded between the date of first dose until the last tumor assessment prior to subsequent therapy (including tumor resection surgery) for the individual subject in the study (Table 11). As with the primary definitions of tumor response, early progression (i.e., irPD occurring prior to Week 8) will not preclude an irBOR of irCR, irPR or irSD resulting from the Week 8 assessment. An assessment of irPD at or after Week 8 will preclude a subsequent irBOR of irCR, irPR or irSD. However, any post-progression clinical activity in subjects with irBOR of irPD may be summarized for exploratory purposes.

Table 11 Immune-Related Best Overall Response (irBOR)

Target Lesions Baseline (Index) and New Measurable Lesions	Non-Target Lesions ^a		irRC Overall Response
	Total Measurable Tumor Burden	Baseline Lesions	
irCR	irCR	No	irCR
irCR	irSD	No	irPR
irPR	irCR or irSD	No	irPR
irSD	irCR or irSD	No	irSD

Target Lesions Baseline (Index) and New Measurable Lesions	Non-Target Lesions ^a		irRC Overall Response
	Total Measurable Tumor Burden	Baseline Lesions	
irPD	Any	Yes or No	irPD
Any	Unequivocal Progression	Yes or No	irPD
Any	Any	Yes	irPD

irCR = immune-related complete response; irPR = immune-related partial response; irSD = immune-related stable disease; irPD = immune-related progressive disease

^a Any increase in the size or number of non-measurable lesions does not necessarily imply an overall response of irPD. If these lesions become measurable (≥ 10 mm) at a subsequent assessment, their measurement will at that point start to contribute to the total measurable tumor burden. To achieve unequivocal progression of non-target lesions, there must be substantial worsening in non-target disease that is of a magnitude that the Investigator feels it is important to change therapy. Equivocal findings of progression of non-target lesions (e.g., small and uncertain new lesions; cystic changes or necrosis in existing lesions) should be considered irSD, and treatment may continue until the next assessment.

7.1.5 Other Procedures

7.1.5.1 Withdrawal/Discontinuation

When a subject discontinues/withdraws prior to trial completion, all applicable activities scheduled for the final trial visit should be performed at the time of discontinuation. Any AEs that are present at the time of discontinuation/withdrawal should be followed in accordance with the safety requirements outlined in [Section 7.2](#) - Assessing and Recording Adverse Events.

Treatment may continue until a study discontinuation criterion is met or for up to 2 years. Subjects who achieve a CR should receive at least 1 additional cycle of treatment.

Any subject who is still deriving clinical benefit from ADXS11-001 therapy at the end of their 2 year treatment period or has achieved CR and subsequently progressed within 1 year of stopping study treatment may be enrolled into a separate extension study, as available.

7.1.6 Visit Requirements

Visit requirements are outlined in [Section 6.1](#) – Schedule of Events. Specific procedure-related details are provided above in [Section 7.1](#) - Trial Procedures.

7.1.6.1 Screening

Screening period – will start when the first screening evaluation is performed. This does not include signing of informed consent or wash out periods. Screening evaluations will be performed within 28 days prior to the first treatment administration, unless otherwise specified.

Informed Consent - each subject must sign a copy of the most current IRB/IEC approved informed consent document. A copy of the signed document will be maintained with the subject's records.

Inclusion/Exclusion Criteria - all inclusion and exclusion criteria will be reviewed by the Investigator or qualified designee to ensure that the subject qualifies for the trial.

Prior/Concomitant Therapies and Procedures - past or current medical conditions, current medications, medications taken within 28 days of study entry, histological confirmation of cancer, tumor staging (refer to the most current American Joint Committee on Cancer Staging Manual, the 5th edition or higher), and prior cancer therapies and best response(s), if applicable.

Pregnancy test - A rapid pregnancy test will be performed for all women of child bearing potential. A positive rapid pregnancy test must be confirmed by serum pregnancy test (minimum sensitivity 25 IU/L or equivalent units of β HCG).

Laboratory Procedures (hematology, chemistry, urinalysis, other) – see [Section 7.1.3](#).

Tumor Imaging/Disease Assessment - CT scan or MRI for determination of unidimensional measurements and disease response. Baseline tumor imaging/disease assessment must be performed within 28 days prior to the first dose of ADXS11-001. Then imaging studies and tumor assessments will be performed every 9 weeks starting on Week 8 of every Cycle.

7.1.6.2 Treatment Period

Subjects should arrive at the study center early on the days of their scheduled treatment in order to be evaluated, have laboratory specimens collected before treatment commences, allow for infusion timing, and take study prophylactic regimen as described in [Section 5.2.4](#).

During the time the subjects are at the study site, the infusion line will be left in place to administer parenteral drugs, if necessary. Subjects will remain at the study center for a minimum of 4 hours after ADXS11-001 administration for safety observation, and if necessary, treatment of side effects. Subjects may receive NSAIDs and antiemetics per label or package insert on Day 1 and Day 2, as needed.

Adverse Event Monitoring - The investigator or qualified designee will assess each subject to evaluate for potential new or worsening AEs as specified in the Schedule of

Events and more frequently if clinically indicated. AE/serious events will be graded, reported and recorded on the eCRF according to NCI CTCAE v 4.0. Toxicities will be characterized in terms regarding seriousness, causality, toxicity grading, and action taken with regard to trial treatment-

Physical Examination - evaluation by body system.

Vital Signs - blood pressure, pulse rate, respiratory rate, and temperature will be checked and recorded prior to administration of ADXS11-001 and every [REDACTED] for the first 4 hours following the infusion. Height and weight will be measured at screening, and weight will be measured pre-dose at every visit.

ECOG Performance Status - according to ECOG criteria.

Laboratory Procedures - according to [Section 7.1.3](#).

Prophylactic Medications – will be pretreated with prophylactic regimen on the day of dosing and completed at least 30 minutes before each ADXS11-001 infusion as outlined in [Section 5.2.3](#).

Prophylactic Antibiotics with Instructions –

(1) During Study Treatment Phase - All subjects will receive a 7 day course of oral antibiotic therapy starting approximately 72 hours (Day 4) after administration of ADXS11-001. Antibiotic therapy should consist of either 160 mg trimethoprim/800 mg sulfamethoxazole (DS) tablet administered three times during the 7 consecutive days or 80 mg trimethoprim/400 mg sulfamethoxazole administered daily for 7 consecutive days or for subjects with sulfa allergies, ampicillin 500 mg four times daily for 7 consecutive days. ADXS11-001 is resistant to both streptomycin and chloramphenicol. In the event a subject experiences a persistent fever present at 72 hours after receiving ADXS11-001, the oral regimen will be replaced by broad spectrum IV antibiotics administration- until a blood culture is obtained and results are available. At this time, a specific IV antibiotic regimen may be prescribed based on the results of the blood culture. Should a diagnosis of listeriosis be made intensive IV antibiotic treatment must be initiated. Ampicillin +/- Gentamicin is the preferred treatment regimen but other IV antibiotics may be used based on the subject's tolerance, culture and sensitivity results. An ID consult should be obtained.

(2) Post Study Treatment - All subjects will receive a 6 month course of oral trimethoprim/sulfamethoxazole or ampicillin for subjects with sulfa allergies to be initiated approximately 72 hours following the last dose of study treatment or at the time of study discontinuation. Trimethoprim/sulfamethoxazole therapy should consist of either 160 mg trimethoprim/800 mg sulfamethoxazole (DS) tablet administered three times a week or 80 mg trimethoprim/400 mg sulfamethoxazole administered daily for 7 consecutive days. The dose of ampicillin consists of 500 mg four times daily for 6 months.

Tumor Imaging/Disease Assessment - CT scan or MRI for determination of unidimensional measurements and disease response. Imaging studies and tumor assessments will be performed every 9 weeks starting at Week 8 of Cycle 1.

Pregnancy test - A rapid pregnancy test will be performed within 72 hours of each treatment administration (combination or monotherapy) for all women of child bearing potential prior to treatment. A positive rapid pregnancy test must be confirmed, prior to dosing, by a serum pregnancy test (minimum sensitivity 25 IU/L or equivalent units of β HCG).

